3.0 Objectives

The purpose of this research is to provide prosthesis prescription guidance for VA clinicians whose patients carry infants, toddlers, and other loads.

The specific aim of this research is to identify the study prosthetic foot that minimizes biomechanical gait deviations when compared to the standard-of-care for veterans with lower limb amputation who carry infants, toddlers, or other loads.

We will conduct a human subject experiment with unilateral transtibial amputees (n=40). Each participant will walk on an instrumented treadmill with no added load and four added load conditions of 13.6 kg: anterior, posterior, intact-side carry, and prosthetic-side carry. Using a

within-subject experimental design with block randomization, each participant will wear: a standard-of-care prosthetic foot, this same prosthetic foot with a heel-stiffening wedge, this same prosthetic foot but one category stiffer, a dual keel prosthetic foot intended for load carriage applications, and a powered ankle-foot purported to adapt to changing loads.

In general, we hypothesize that one of these prosthetic feet will minimize biomechanical deviations for (1) no added load, (2) anterior added load, (3) posterior added load, (4) intact-side carry load, and (5) prosthetic-side carry load.

Our specific hypotheses for each load condition are:

H1 a study prosthesis exists that maximizes the vertical GRF impulse (a measure of body support),

H2 a study prosthesis exists that maximizes the anterior GRF impulse (a measure of body forward propulsion),

H3 a study prosthesis exists that minimizes the peak-to-peak range of sagittal plane whole-body angular momentum (a measure of balance control primarily for anterior and posterior added load conditions),

H4 a study prosthesis exists that minimizes the peak-to-peak range of frontal plane whole-body angular momentum (a measure of balance control primarily for intact-side and prosthetic-side added load conditions), and

H5 a study prosthesis exists that minimizes the mechanical energy expenditure (allow for more efficient locomotion).

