5.6 Data Analysis

Kinematic and kinetic data from the experiment will be processed in Visual 3D (C-Motion Inc., Germantown, MD) and aggregated using custom project specific software (Matlab; Mathworks, Natick, MA). To determine changes in walking performance, we will calculate biomechanical quantities related to body support, forward propulsion and balance control including: the vertical ground reaction force (GRF) impulse, the anterior GRF impulse, and the peak-to-peak range of the frontal and sagittal whole-body angular momentum. We will also calculate mechanical energy expenditure (i.e., the sum of the joint mechanical work of each leg). The GRF and joint work metrics will be normalized by body weight and added load while whole-body angular momentum will be normalized by body weight and added load, walking speed and leg length.

Linear mixed-effects regressions will be used to detect differences in the biomechanical quantities (dependent variables) between study prostheses (independent variables) for each load condition separately (anterior, posterior, intact-side carry, and prosthetic-side carry) following an assessment of normality. This method allows inclusion of subjects who do not complete all study procedures (repeated measures analysis of variance (ANOVA) models do not). These analyses will test for differences between the study prostheses across the four different load carriage conditions with random effects for subject and subject by study prosthesis interaction. If the data is not normally distributed, we will consult with our biostatistician on an appropriate transform. An omnibus test for significance will be generated using a likelihood ratio test with an alpha level of 0.05. Individual pair-wise differences will be assessed using simultaneous inference and associated 95% confidence intervals. All statistical analyses will be performed by study staff using existing VA enterprise software (SPSS Statistics v22; IBM, Inc.). Exact p-values will be reported for each test.

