## Statistical Analysis Plan

Outcome metrics: vertical GRF impulse, anterior GRF impulse, peak-to-peak range of sagittal plane whole body angular momentum (WBAM), and peak-to-peak range of frontal plane WBAM.

Linear mixed effects regression was used to assess differences in biomechanical outcomes (the dependent variable) by foot type for each load by combining all loading conditions in a single model and using a foot type by load condition interaction to estimate means and mean differences in outcomes by foot for each load separately. This model assumes a common variance in outcomes across load and foot. Thus, standard errors for the means will be similar across load and foot. Subject and foot type within subject were considered random effects. Several random effects structures were considered (from subject ID intercept only to a full subject by foot interaction model) with the best model chosen based on likelihood ratio tests. Hypothesis testing for the overall association between outcome and foot type were carried out using conditional F-tests for each load type. For comparison, the Benjamini Hochberg (BH) adjustment was also applied to the F-tests for each model across the 5 load conditions to maintain a false discovery rate of 5%. Hypothesis testing for pairwise differences across feet was carried out using Tukey's method to account for the inflation of the Type 1 error due to assessment of 10 pairwise differences for each load. Analyses were carried out using R 4.2.3 (R Foundation for Statistical Computing, Vienna, Austria) and packages tidyverse, lme4, emmeans and lmerTest.

Outcome metrics: positive net ankle joint work.

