Linear mixed-effects regression was used to assess differences in biomechanical outcome (i.e., prosthetic limb joint work over the entire gait cycle as dependent variable) by prosthetic foot for each load condition. All loads were combined in a single model with a foot-by-load interaction to estimate means and mean differences in outcome by foot within each load. The model assumed a common variance, yielding similar standard errors (SE) across loads and feet. Participant and foot within participant were included as random effects. Multiple random effects structures were compared using likelihood ratio tests to select the best-fitting model. The dependent variable was transformed when residual heteroscedasticity was detected. Hypothesis testing for the overall associations between foot and outcome variables were performed using conditional F-tests for each load. For comparison, the Benjamini-Hochberg correction was also applied across the loads to control the false discovery rate at 5%. Hypothesis testing for pairwise differences across feet was performed using Tukey method to account for the inflation of the Type-1 error due to multiple testing (10 comparisons per load). All analyses were conducted in R v4.2.3 (R Foundation for Statistical Computing, Vienna, Austria) using the following packages: tidyverse, lme4, emmeans, and lmerTest.

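### The SAP contains no analysis for hypothesis H5 (mechanical energy expenditure), and its only work outcome is confined to the prosthetic side

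*SAP*

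**What the plan says.** **Protocol, 3.0 Objectives.** The hypotheses are introduced with "Our specific hypotheses for each load condition are", and five follow. The last reads "H5 a study prosthesis exists that minimizes the mechanical energy expenditure (allow for more efficient locomotion".

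**Protocol, 5.6 Data Analysis.** After the two ground reaction force (GRF) impulses and the two angular momentum ranges, the text adds "We will also calculate mechanical energy expenditure (i.e., the sum of the joint mechanical work of each leg". It fixes the scaling: "The GRF and joint work metrics will be normalized by body weight and added load". It then gives the analysis: "Linear mixed-effects regressions will be used to detect differences in the biomechanical quantities (dependent variables) between study prostheses".

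**SAP, first outcome block.** The list opens "Outcome metrics: vertical GRF impulse, anterior GRF impulse, peak-to-peak range of sagittal plane whole body angular momentum (WBAM" and closes with the frontal-plane range. That makes four outcomes.

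**SAP, second outcome block.** The heading is "Outcome metrics: positive net ankle joint work". The model text describes the outcome as "prosthetic limb joint work over the entire gait cycle as dependent variable".

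The SAP does not use the term mechanical energy expenditure, does not sum work across legs, does not mention intact-limb work and does not refer to H5.

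**The concern.** One of the five stated hypotheses has no analysis in the SAP, and a work outcome that the protocol does not name appears in its place. The SAP explains neither change. If the SAP is what is followed, the study will have no result on which foot gives the lowest mechanical energy expenditure.

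There is also a risk that the ankle-work result is read as the answer to H5, since it is the only work outcome reported. It cannot serve as that answer, for two reasons drawn from the protocol's own Introduction (2.0):

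- Amputees carrying loads are said to show more joint power generation and absorption in the intact limb. The SAP's work outcome leaves that limb out.
- The energy storage and release of the prosthetic foot is described as helping locomotion. Less work at the prosthetic ankle therefore does not by itself mean the lower total expenditure that H5 seeks.

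The study is meant to guide prescription, and efficiency of locomotion is one of the properties it set out to compare.

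**Working it through.** The check is a comparison of text plus a count. The plan gives no figure to reproduce: the power calculations in Protocol 5.6 cover H1 and H2 only.

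**Step 1. Match each hypothesis to its quantity and its SAP outcome.**

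| Hypothesis (Protocol 3.0) | Quantity (Protocol 5.6) | In the SAP? |
|---|---|---|
| H1 | vertical GRF impulse | yes, block 1 |
| H2 | anterior GRF impulse | yes, block 1 |
| H3 | sagittal angular momentum range | yes, block 1 |
| H4 | frontal angular momentum range | yes, block 1 |
| H5 | mechanical energy expenditure | no |

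Carried over: 4 of 5. Added without a counterpart in the protocol: 1 (ankle work).

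**Step 2. Ask whether block 2 could be H5 under another name.** Two phrases are open to interpretation, so each reading is tried.

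- The protocol's definition may mean one total over both legs. That total needs the intact leg, which is absent. Coverage is 0 of 1.
- It may mean one sum for each leg. The intact-leg sum is absent. Coverage is at most 1 of 2, and only if the block 2 model text refers to all joints of the prosthetic limb, which its heading (ankle only) contradicts.
- The block 2 heading may mean positive work only, or signed net work. Either way the variable belongs to the prosthetic side.

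Intact-limb work is covered in none of these.

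**Step 3. Check the standing of H5.** The Secondary Analyses part of Protocol 5.6 covers satisfaction and EMG only. H5 appears in the same list as H1 to H4, with the same claim for every load condition.

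**Step 4. Size the gap.** The SAP tests foot type once per load over 5 load conditions, with 10 pairwise comparisons per load. For one H5 variable the missing output is 5 × 1 = 5 F-tests and 5 × 10 = 50 pairwise comparisons. With one variable per leg it would be 2 × 5 = 10 and 2 × 50 = 100.

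**Step 5. Check for lost text.** Both SAP blocks have an outcome line and a full methods paragraph, with no sign of redaction, so the omission does not look like a product of text extraction.

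**The case against.** The strongest objection is that the protocol may never have promised a test of this quantity. In Protocol 5.6 the term for the biomechanical quantities introduces four metrics, and energy expenditure follows in a separate sentence that says only that it will be calculated. Read narrowly, the regressions apply to the four metrics, which is what SAP block 1 contains. This reading is possible, but it would leave a stated hypothesis with no test anywhere in the plan, which is no better. The wider reading fits the Objectives.

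Second, the SAP does not say that it replaces Protocol 5.6, so the protocol's definition still stands. That is fair, and it is why the loss of a result is stated as conditional on following the SAP. The two documents still disagree, and nothing reconciles them.

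Third, the SAP is written mostly in the past tense and reads as a record of analyses done. This stands, and it affects the remedy: an H5 model added now should be labelled as specified in the protocol but added late.

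Fourth, the SAP never links ankle work to H5, so the risk of misreading is a judgement, not a fact. That is also fair. The omission does not depend on it, nor on the inference from the Introduction about energy storage and release.

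Finally, the unclear definition of the ankle variable is a separate matter from the H5 omission. It is a minor wording point, taken up here only because it bears on whether block 2 could stand in for H5.

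**Conclusion.** The concern holds. The SAP carries 4 of the protocol's 5 quantities and omits the one that H5 needs, without saying so. Its work outcome covers 0 of 1 of the H5 quantity if that is a both-leg total, and at most 1 of 2 if it is one sum per leg. The conclusion rests on the wording of the two documents and on no assumed figures.

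This should be fixed, but it does not threaten the whole study. H1 to H4 are unaffected, H5 is not designated primary, and no size of bias can be computed because no joint-work values are given.

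**What to change.** 1. Add the energy expenditure quantity from Protocol 5.6 to the SAP as the H5 outcome, in the same foot-by-load mixed model and with the protocol's scaling by body weight and added load. Check residuals, and apply the transformation rule in SAP block 2 if it is needed.
2. State whether the quantity is one total over both legs or one sum per leg. If it is per leg, analyse both. State how positive and negative work are combined.
3. If the other analyses are already complete, label the H5 model as protocol-specified but added late.
4. If H5 was deliberately dropped or replaced, say so, with the reason and the timing. Label ankle work as an outcome introduced after the protocol, and do not present it as the test of H5.
5. Give the ankle-work variable one definition in both heading and model text: which joint, which limb, and positive-only or signed net work.

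The cost is SAP wording, derivation of the work sum, and one more model fit (two if per leg). The full-body marker set and the two treadmill force plates in Protocol 5.5 are already planned, so no new data collection should be needed, provided that the recorded data are usable for the joints of both legs.
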